5.6 STUDY ASSESSMENTS

Signed, IRB-approved informed consent must be obtained from patients prior to the pretreatment assessments. The schedule of activities to be performed during the study is provided in Appendix 1. All activities must be performed and documented for each patient. Patients will be closely monitored for safety and tolerability throughout the study. Patients should be assessed for toxicity prior to each dose; dosing will occur only if the clinical assessment and local laboratory test values are acceptable.

5.6.1 Informed Consent Forms and Screening Log

Written informed consent for participation in the study must be obtained before performing any study-related procedures (including screening evaluations). Informed Consent Forms for enrolled patients and for patients who are not subsequently enrolled will be maintained at the study site.

All screening evaluations must be completed and reviewed to confirm that patients meet all eligibility criteria before enrollment. The investigator will maintain a screening log to record details of all patients screened and to confirm eligibility or record reasons for screening failure, as applicable.

Re-screening is required if a patient has not met all of the eligibility criteria within 28 days from the original date of the screening visit. Re-screening refers to repeating the entire screening process with the exception of performing a repeat biopsy to collect a tumor tissue sample to be used to determine PD-L1 status and repeating CT and/or MRI imaging scans used for tumor assessment, provided the biopsy tissue sample and imaging scans were obtained during the original screening visit. Patients are only allowed to be re-screened twice. Blood samples may be redrawn due to sample handling problems, breakage, or sample integrity, without being considered a re-screen.

5.6.2 Medical History, Concomitant Medication, and Demographic Data

Medical history, including clinically significant diseases, surgeries, cancer history (including prior cancer therapies and procedures), reproductive status, smoking history, and use of alcohol and drugs of abuse, will be recorded at baseline. In addition, all medications (e.g., prescription drugs, over-the-counter drugs, vaccines, herbal or homeopathic remedies, nutritional supplements) used by the patient within 7 days prior to initiation of study treatment will be recorded. At the time of each follow-up physical examination, an interval medical history should be obtained and any changes in medications and allergies should be recorded.

Demographic data will include age, sex, and self-reported race/ethnicity.

5.6.3 Physical Examinations

A complete physical examination, performed at screening and other specified visits, should include an evaluation of the head, eyes, ears, nose, and throat, and the cardiovascular, dermatological, musculoskeletal, respiratory, gastrointestinal, and neurological systems. Any abnormality identified at baseline should be recorded on the General Medical History and Baseline Conditions eCRF.

Limited, symptom-directed physical examinations should be performed at specified postbaseline visits and as clinically indicated. Changes from baseline abnormalities should be recorded in patient notes. New or worsened clinically significant abnormalities should be recorded as adverse events on the Adverse Event eCRF.

5.6.4 Vital Signs

Vital signs will include measurements of respiratory rate, pulse rate, and systolic and diastolic blood pressure while the patient is in a seated position, and temperature. Height will be assessed at baseline, and weight will be assessed at each study visit.

Vital signs should be measured within 60 minutes prior to each study treatment infusion and, if clinically indicated, during or after the infusion. In addition, vital signs should be measured at other specified timepoints as outlined in the schedule of activities (see Appendix 1).

5.6.5 Tumor and Response Evaluations

Patients will undergo tumor assessments at baseline and every 8 weeks in all cohorts assessed, regardless of dose delays, until radiographic disease progression per RECIST v1.1 or (for atezolizumab treated patients who continue treatment after radiographic disease progression) loss of clinical benefit as determined by the investigator. Thus, tumor assessments are to continue according to schedule in patients who discontinue treatment for reasons other than disease progression or loss of clinical benefit, even if they start new anti-cancer therapy. At the investigator's discretion, tumor assessments may be repeated at any time if progressive disease is suspected.

All measurable and evaluable lesions should be assessed and documented at screening. Tumor assessments performed as standard of care prior to obtaining informed consent and within 28 days prior to initiation of study treatment do not have to be repeated at screening.

Cross sectional imaging will be performed with either contrast enhanced CT or MRI. RECIST 1.1 criteria will be used to determine disease response.

If a CT scan for tumor assessment is performed in a positron emission tomography (PET)/CT scanner, the CT acquisition must be consistent with the standards for a full contrast diagnostic CT scan.

All measurable and evaluable lesions should be re assessed at each subsequent tumor evaluation. The same radiographic procedures used to assess disease sites at screening should be used for subsequent tumor assessments (e.g., the same contrast protocol for CT scans).

Response will be assessed by a blinded radiologist at the MD Anderson Quantitative Imaging Analysis Core using RECIST v1.1 (see Appendix 2) and immune-modified RECIST (see Appendix 5). Assessments should be performed by the same evaluator, if possible, to ensure internal consistency across visits. Results must be reviewed by the investigator before dosing at the next cycle.

For cutaneous squamous cell carcinoma, since “surgery (preferable) or definitive radiation therapy (with or without radiosensitizing agent)” is allowed for patients after initial response, such a definitive local therapy can only be performed after at least 1 tumor assessment.

5.6.6 Laboratory, Biomarker, and Other Biological Samples

Samples for the following laboratory tests will be sent to the study site's local laboratory for analysis:

- Hematology: WBC count, RBC count, hemoglobin, hematocrit, platelet count, differential count (neutrophils, eosinophils, basophils, monocytes, lymphocytes, other cells)
- Chemistry panel (serum or plasma): sodium, potassium, magnesium, chloride, bicarbonate, glucose, BUN or urea, creatinine, total protein, albumin, phosphorus, calcium, total bilirubin, alkaline phosphatase, ALT, AST, LDH, CPK
- Coagulation: INR, aPTT, fibrinogen, D-dimer
- Thyroid function testing: thyroid-stimulating hormone, free triiodothyronine (T3) (or total T3 for sites where free T3 is not performed), free thyroxine (also known as T4)
- HIV serology
- HBV serology: HBsAg, hepatitis B surface antibody, total HBcAb. If a patient has a negative HBsAg test and a positive total HBcAb test at screening, an HBV DNA test should be performed at screening.
- HCV serology: HCV antibody and (if HCV antibody test is positive) HCV RNA. If a patient has a positive HCV antibody test at screening, an HCV RNA test must also be performed to determine if the patient has an active HCV infection.
- Pregnancy test. All women of childbearing potential will have a serum/urine pregnancy test at screening. A woman is considered to be of childbearing potential if she is postmenarcheal, has not reached a postmenopausal state (≥ 12 continuous months of amenorrhea with no identified cause other than menopause), and has not undergone surgical sterilization (removal of ovaries and/or uterus).
- Urinalysis (pH, specific gravity, glucose, protein, ketones, and blood); dipstick permitted
- *The following samples will be sent to one or several central laboratories or to the Genentech Inc. for analysis:*
- **Blood** samples for translational research on biomarkers (See Appendix 9).
- Tumor tissue samples will be collected for exploratory research on biomarkers (See Appendix 9).

- a. Fresh tumor tissue sample (or archival tissue) will be collected at baseline for determination of PD L1 expression and for exploratory research on biomarkers
 - Tissue should be collected by excisional or core needle biopsy, typically using a 21-18 gauge needle. The biopsy should include at least 5 cores, 2 FFPE and 3 fresh frozen. It should be collected within 28 days prior to initiation of protocol therapy.
 - For archival tissue: a representative FFPE tumor specimen in a paraffin block (preferred) or at least 10 slides containing unstained, freshly cut, serial sections need to be submitted along with an associated pathology report. Tumor tissue should be of good quality based on total and viable tumor content. Samples should ideally contain a minimum of 50 viable tumor cells that preserve cellular context and tissue architecture regardless of needle gauge or retrieval method. Samples collected via resection, core-needle biopsy (at least three cores, embedded in a single paraffin block), or excisional, incisional, punch, or forceps biopsy are acceptable.
 - Considering the benefit seen with immunotherapy in MSI-H colon cancer, we will perform MSI tests on patients with small bowel and appendiceal adenocarcinoma.
- b. Tumor tissue sample will also be collected at week 4 for exploratory research on biomarkers
 - Biopsies at week 4 should be performed within 7 days before administration of C2D1 of study therapy. Samples collected via resection, core-needle biopsy (at least three cores preferred), or excisional, incisional, punch, or forceps biopsy are preferred.
- c. Tumor tissue sample will also be collected at time of progression for exploratory research on biomarkers
 - Biopsies at the time of progression should be performed within 40 days after progression or prior to the next anti-cancer therapy, whichever is sooner. Samples collected via resection, core-needle biopsy (at least three cores preferred), or excisional, incisional, punch, or forceps biopsy are preferred.
 - For cutaneous squamous cell carcinoma, where local therapy options may be considered in the future, the lesions biopsied will be documented at each time point and if possible, a sample will be collected in patients who go to surgery. The location of the sample collected at surgery will also be documented.

Blood and tissue collections will be tracked by Tissue Station. Collection requests will be placed in the system, prior collections, and updated once completed including details of the process. All samples shipped to Genentech will be tracked and documented in Tissue Station,

Exploratory biomarker research may include, but will not be limited to, immunohistochemistry for PD-L1, multiplexed immunofluorescence for immune markers, flow cytometry, analysis of ctDNA concentration, genes or gene signatures associated with tumor immunobiology, PD-L1, lymphocyte subpopulations, T-cell receptor repertoire, or cytokines associated with T-cell activation and may involve DNA or RNA extraction, analysis of germline or somatic mutations, and use of WGS or NGS.

For sampling procedures, storage conditions, and shipment instructions, see the laboratory manual.

Biological samples will be destroyed when the final manuscript has been completed, with the following exceptions:

- Blood samples collected for WGS will be stored until they are no longer needed or until they are exhausted. However, the storage period will be in accordance with the IRB/EC-approved Informed Consent Form and applicable laws (e.g., health authority requirements).
- **Blood, plasma, serum, and tumor tissue** samples collected for biomarker research will be destroyed no later than 5 years after the final manuscript has been completed.

When a patient withdraws from the study, samples collected prior to the date of withdrawal may still be analyzed, unless the patient specifically requests that the samples be destroyed or local laws require destruction of the samples.

Data arising from sample analysis will be subject to the confidentiality standards.

Given the complexity and exploratory nature of exploratory biomarker analyses, data derived from these analyses will generally not be provided to study investigators or patients unless required by law.

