8. Left ventricular ejection fraction (LVEF) $<$ institutional lower limit of normal or $<$ 50%.
9. History or risk of autoimmune disease, including but not limited to systemic lupus erythematosus, rheumatoid arthritis, inflammatory bowel disease, vascular thrombosis associated with antiphospholipid syndrome, Wegener's granulomatosis, Sjögren's syndrome,

Bell's palsy, Guillain-Barré syndrome, multiple sclerosis, autoimmune thyroid disease, vasculitis, or glomerulonephritis

- a. Patients with a history of autoimmune hypothyroidism on a stable dose of thyroid replacement hormone may be eligible.
- b. Patients with controlled Type 1 diabetes mellitus on a stable insulin regimen may be eligible.
- c. Patients with eczema, psoriasis, lichen simplex chronicus or vitiligo with dermatologic manifestations only (e.g., patients with psoriatic arthritis would be excluded) are permitted provided that they meet the following conditions:
 - i. Patients with psoriasis must have a baseline ophthalmologic exam to rule out ocular manifestations
 - ii. Rash must cover less than 10% of body surface area (BSA)
 - iii. Disease is well controlled at baseline and only requiring low potency topical steroids (e.g., hydrocortisone 2.5%, hydrocortisone butyrate 0.1%, flucinolone 0.01%, desonide 0.05%, aclometasone dipropionate 0.05%)
 - iv. No acute exacerbations of underlying condition within the last 12 months (not requiring psoralen plus ultraviolet A radiation [PUVA], methotrexate, retinoids, biologic agents, oral calcineurin inhibitors; high potency or oral steroids)

10. History of idiopathic pulmonary fibrosis, pneumonitis (including drug induced), organizing pneumonia (i.e., bronchiolitis obliterans, cryptogenic organizing pneumonia, etc.), or evidence of active pneumonitis on screening chest computed tomography (CT) scan

- a. History of radiation pneumonitis in the radiation field (fibrosis) is permitted.

11. History of HIV infection or active hepatitis B (chronic or acute) or hepatitis C infection.

- a. Patients with past or resolved hepatitis B infection (defined as having a negative hepatitis B surface antigen [HBsAg] test and a positive anti-HBc [antibody to hepatitis B core antigen] antibody test) are eligible.
- b. Patients positive for hepatitis C virus (HCV) antibody are eligible only if polymerase chain reaction (PCR) is negative for HCV RNA.

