- History or risk of autoimmune disease, including but not limited to systemic lupus erythematosus, rheumatoid arthritis, inflammatory bowel disease, vascular thrombosis associated with antiphospholipid syndrome, Wegener's granulomatosis, Sjögren's

syndrome, Bell's palsy, Guillain-Barré syndrome, multiple sclerosis, autoimmune thyroid disease, vasculitis, or glomerulonephritis

- a. Patients with a history of autoimmune hypothyroidism on a stable dose of thyroid replacement hormone may be eligible.
 - b. Patients with controlled Type 1 diabetes mellitus on a stable insulin regimen may be eligible.
 - c. Patients with eczema, psoriasis, lichen simplex chronicus or vitiligo with dermatologic manifestations only (e.g., patients with psoriatic arthritis would be excluded) are permitted provided that they meet the following conditions:
 - Patients with psoriasis must have a baseline ophthalmologic exam to rule out ocular manifestations
 - Rash must cover less than 10% of body surface area (BSA)
 - Disease is well controlled at baseline and only requiring low potency topical steroids (e.g., hydrocortisone 2.5%, hydrocortisone butyrate 0.1%, flucinolone 0.01%, desonide 0.05%, aclometasone dipropionate 0.05%)
 - No acute exacerbations of underlying condition within the last 12 months (not requiring psoralen plus ultraviolet A radiation [PUVA], methotrexate, retinoids, biologic agents, oral calcineurin inhibitors; high potency or oral steroids)
- History of idiopathic pulmonary fibrosis, pneumonitis (including drug induced), organizing pneumonia (i.e., bronchiolitis obliterans, cryptogenic organizing pneumonia, etc.), or evidence of active pneumonitis on screening chest computed tomography (CT) scan
 - a. History of radiation pneumonitis in the radiation field (fibrosis) is permitted.
- History of HIV infection or active hepatitis B (chronic or acute) or hepatitis C infection.
 - a. Patients with past or resolved hepatitis B infection (defined as having a negative hepatitis B surface antigen [HBsAg] test and a positive anti-HBc [antibody to hepatitis B core antigen] antibody test) are eligible.
 - b. Patients positive for hepatitis C virus (HCV) antibody are eligible only if polymerase chain reaction (PCR) is negative for HCV RNA.
- Active tuberculosis or severe infections within 4 weeks prior to Cycle 1, Day 1, including but not limited to hospitalization for complications of infection, bacteremia, or severe pneumonia

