^b Atezolizumab may be withheld for a period of time beyond 12 weeks to allow for corticosteroids to be reduced to ≤ 10 mg/day oral prednisone or equivalent. The acceptable length of the extended period of time must be agreed upon by the investigator and the Medical Monitor.

^c Resumption of atezolizumab may be considered in patients who are deriving benefit and have fully recovered from the immune-related event. Patients can be rechallenged with atezolizumab only after approval has been documented by both the investigator (or an appropriate delegate) and the Medical Monitor.

HEPATOTOXICITY

Hepatotoxicity has been associated with the administration of atezolizumab and cobimetinib. Eligible patients must have adequate liver function, as manifested by measurements of total bilirubin and hepatic transaminase, and liver function will be monitored throughout study treatment.

While in this study, patients presenting with right upper-quadrant abdominal pain and/or unexplained nausea or vomiting should have liver function tests (LFTs) performed immediately and reviewed before administration of the next dose of study drug.

If LFTs increase, neoplastic, concurrent medications, viral hepatitis, and toxic etiologies should be considered and addressed, as appropriate. Imaging of the liver, gall bladder, and biliary tree should be performed to rule out neoplastic or other causes for the increased LFTs. Anti-nuclear antibody, perinuclear anti-neutrophil cytoplasmic antibody, anti-liver kidney microsomal antibodies, and anti-smooth muscle antibody tests should be considered.

Patients with LFT abnormalities should be managed according to the guidelines in

[Table A3-2](#).

Table A3-2 Guidelines for Managing Atezolizumab and Cobimetinib–Associated Hepatotoxicity

Event	Action to Be Taken
Elevations in ALT, AST, and/or bilirubin	

AST/ALT > ULN to $\leq 3 \times$ ULN with total bilirubin $< 2 \times$ ULN (Grade 1)	
 Continue atezolizumab and cobimetinib. Continue with the standard monitoring plan (i.e., LFTs q4w before dosing).

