AST/ALT > $3 \times$ baseline values to $< 5 \times$ ULN with total bilirubin $< 2 \times$ ULN (Grade 2)	
 Continue all study treatment. Monitor LFTs at least weekly. Consider referral to a hepatologist and liver biopsy. For suspected immune related events of > 5 days duration 
 Consider withholding atezolizumab^c Consider administering 1-2 mg/kg/day oral prednisone or equivalent followed by ≥ 1 month taper Restart atezolizumab if event resolves to Grade 1 or better within 12 weeks^{a, b} Permanently discontinue atezolizumab and cobimetinib if event does not resolve to Grade 1 or better within 12 weeks^{a, b, c}
AST/ALT > $5 \times$ baseline values to $< 10 \times$ ULN with total bilirubin $< 2 \times$ ULN (Grade 3)	
 Continue all study treatment. Monitor LFTs at least weekly. Consider referral to a hepatologist and liver biopsy. For suspected immune related events 
 Withhold atezolizumab Consider administering 1-2 mg/kg/day oral prednisone or equivalent followed by ≥ 1 month taper If event does not improve within 48 hours after initiating corticosteroids, consider adding an immunosuppressive agent. If event resolves to Grade 1 or better, taper corticosteroids over ≥ 1 month. Permanently discontinue atezolizumab and cobimetinib if event does not resolve to Grade 1 or better within 12 weeks^{a, b, c}
AST/ALT > $3 \times$ ULN with bilirubin $> 2 \times$ ULN	
 Withhold atezolizumab and cobimetinib. Consult hepatologist and consider liver biopsy. Consider administering 1-2 mg/kg/day oral prednisone or equivalent followed by ≥ 1 month taper (for possible autoimmune hepatitis). If LFTs do not decrease within 48 hr after initiation of systemic steroids, consider adding an immunosuppressive agent (e.g., mycophenolate or TNF-α antagonist). Monitor LFTs every 48–72 hr until decreasing and then follow weekly. Restart atezolizumab at fixed dose and cobimetinib at 1 dose reduction after discussion with medical monitor if AST/ALT $< 3 \times$ ULN with bilirubin $< 2 \times$ ULN and steroid dose < 10 mg oral prednisone equivalent per day.^{a, b, c} Permanently discontinue atezolizumab and cobimetinib for life-threatening hepatic events, and contact the Medical Monitor.

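### Patients with resolved hepatitis B serology are eligible whatever their HBV DNA result, although the protocol asks for that test in exactly this group

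*Combined protocol and SAP*

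**What the plan says.** The parent exclusion, item 11 of the synopsis general exclusions and an unnumbered bullet in section 5.1.2, bars "History of HIV infection or active hepatitis B (chronic or acute) or hepatitis C infection". It does not define *active* and does not mention HBV DNA.

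Two sub-items follow, worded the same in both places:

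- **Hepatitis B (11a).** "Patients with past or resolved hepatitis B infection (defined as having a negative hepatitis B surface antigen [HBsAg] test" together with a positive anti-HBc antibody test) are declared eligible. No further condition is attached.
- **Hepatitis C (11b).** Patients with HCV "antibody are eligible only if polymerase chain reaction (PCR) is negative for HCV RNA".

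Section 5.6.6 then sets the follow-on tests. For a negative HBsAg with a positive total HBcAb, "an HBV DNA test should be performed at screening"; no purpose, threshold or consequence is given. For a positive HCV antibody, "an HCV RNA test must also be performed to determine if the patient has an active HCV infection".

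On timing, section 5.6.1 states: "All screening evaluations must be completed and reviewed to confirm that patients meet all eligibility criteria before enrollment".

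**The concern.** The test and the eligibility rule for hepatitis B are not connected. The protocol asks for a viral load measurement in a defined group and then admits that group on two serology results, whatever the measurement shows. A patient with detectable HBV DNA meets 11a word for word while arguably meeting the parent exclusion. Two investigators could decide differently on the same patient and both cite the protocol.

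The stake is patient safety. Appendix 6 states: "Hepatotoxicity has been associated with the administration of atezolizumab and cobimetinib". For a Grade 3 transaminase rise with bilirubin below 2 × ULN, it keeps study treatment going in general. If an immune cause is suspected, it has atezolizumab withheld and prednisone at 1–2 mg/kg/day considered, and adds: "If event does not improve within 48 hours after initiating corticosteroids, consider adding an immunosuppressive agent". If a viral hepatitis were read as an immune event, a patient with unresolved infection could be given immunosuppression, and the event could be wrongly attributed to the study drugs.

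**Working it through.** The plan states no figure on this point, so the main check is a comparison of the text. The arithmetic comes second and only sizes the problem.

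**1. Is it the same group in both places?** Yes. 11a describes HBsAg-negative, anti-HBc-positive patients. Section 5.6.6 triggers the DNA test on negative HBsAg and positive total HBcAb.

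**2. The two viruses side by side.**

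| | Hepatitis B | Hepatitis C |
|---|---|---|
| Eligibility (synopsis 11a/11b; 5.1.2) | Eligible on serology | Eligible only if HCV RNA is negative |
| Follow-on test (5.6.6) | HBV DNA *should* be done | HCV RNA *must* be done |
| Stated purpose of the test | None | To determine active infection |
| Consequence of a positive result | None stated | Not eligible |

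**3. Is the result used anywhere else?** No. HBV DNA is not mentioned elsewhere in the supplied text. The Appendix 1 flowchart lists only viral serology, and only at screening, so no on-treatment HBV testing is scheduled.

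**4. Does the pre-enrollment review close the gap?** Section 5.6.1 has results reviewed against the eligibility criteria. No criterion names HBV DNA, so the reviewer has only the undefined term *active hepatitis B* to apply, and 11a points the other way.

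**5. Size.** The enrollment of n = 60 is the protocol's. The documents give neither prevalence, so both are assumptions:

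- s = proportion with this serology: 5% (range 2% to 10%)
- v = proportion of those who are DNA-positive: 5% (range 2% to 10%)

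Formulas: number tested = n·s; expected DNA-positive = n·s·v; P(at least one) = 1 − (1 − s·v)^n.

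| s | v | Tested | Expected DNA-positive | P(at least one) |
|---|---|---|---|---|
| 2% | 2% | 60 × 0.02 = 1.2 | 1.2 × 0.02 = 0.024 | 1 − 0.9996^60 = 0.024 |
| 5% | 5% | 60 × 0.05 = 3.0 | 3.0 × 0.05 = 0.15 | 1 − 0.9975^60 = 0.139 |
| 10% | 10% | 60 × 0.10 = 6.0 | 6.0 × 0.10 = 0.6 | 1 − 0.99^60 = 0.453 |

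The end rows pair both low and both high values, so they are the extremes of the assumed ranges. The counts are of DNA-positive patients among those who satisfy 11a. They are not counts of patients harmed, and they take no account of investigators who would exclude such a patient on their own judgment.

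**The case against.** The strongest answer is that the protocol, read as a whole, already deals with this. The parent criterion excludes active hepatitis B; 11a clarifies it and does not say that it overrides it. The DNA result is available at screening and must be reviewed before enrollment. On that reading only a cross-reference is missing. This stands in part: an investigator can exclude a DNA-positive patient. But 11a defines resolved infection by serology alone, so the specific rule for this group says the patient may enter.

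The *should*/*must* contrast is the weaker part of the concern. Section 5.6 makes the scheduled activities mandatory, and the DNA test sits within the HBV serology item of 5.6.6. Appendix 1 does not name HBV DNA, however, and even a mandatory test would have no stated consequence.

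There are other safeguards. Liver enzyme limits apply at entry. Chemistry is scheduled on Day 15 of Cycle 1 and on Days 1 and 15 from Cycle 2. Appendix 6 asks that viral hepatitis be considered when liver tests rise, and its steroid guidance for Grade 3 rises is limited to suspected immune events. Section 5.8 lets the investigator withdraw a patient on safety grounds. These limit the harm, but they act after treatment has begun and do not replace an entry rule.

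The documents do not say that either drug, or the management of its toxicity, reactivates hepatitis B. That is correct, and the point does not depend on it: the protocol itself chose to exclude active hepatitis B, and 11a leaves a way around that choice.

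Finally, both prevalences are assumed, and the expected number is well below one. That is accepted. It bears on how large the point is, not on whether the rule is incomplete.

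**Conclusion.** The concern holds. The hepatitis B rule asks for a test and gives its result no role, while the hepatitis C rule beside it is complete. Followed literally, 11a admits a DNA-positive patient despite the exclusion of active hepatitis B. Confidence in this reading is high, since it rests on the text alone.

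The number affected is unknown and probably very small: 0.15 patients expected in 60, with about a 14% chance of at least one, under the assumed 5% and 5%. Across the assumed ranges the expectation runs from 0.024 to 0.6 and the chance from about 2% to 45%. No sample size, power, type I error or response-rate figure changes, and no effect on the toxicity stopping rule has been shown. It should be corrected because it concerns the safety of individual patients and the correction is small.

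**What to change.** 1. In synopsis exclusion 11a and the matching sub-item in section 5.1.2, make eligibility conditional on a negative HBV DNA result at screening, or a level below a threshold the investigators set, in the same form as the hepatitis C sub-item.
2. In section 5.6.6, change *should* to *must* for the HBV DNA test.

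No new timing rule is needed, because section 5.6.1 already requires screening results to be complete and reviewed before enrollment.

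The wording cost is one clause in two places and one word in a third, for a test the protocol already calls for. Because eligibility changes, it needs a protocol amendment with the approvals described in section 9.5, so it is sensibly combined with the next amendment. The cost in accrual is that a rare DNA-positive patient becomes ineligible: 0.15 of 60 expected (range 0.024 to 0.6) under the stated assumptions.
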